### **6.2 Full Analysis Set**

For efficacy, all subjects who have had at least one dose of medication will be included in the ITT analysis. The ITT analysis is defined as the first line efficacy analysis.

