### **8.2.8 TCD**

The result of the TCD central assessment ([name], Münster) is a key element for the efficacy analysis of the study, see 8.4

The technical possibility to perform TCD (sufficient bone window) determines whether a patient is eligible for the study.

- TCD assessment was successful

Due to high rate of no microembolic signals we abandoned the criterion that if no microembolic signal was detected during the recording period then the patient was rated not eligible during the course of the study. In the further course of the study patients were included irrespective whether they present with microemboli or not.

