### 8.4.1 Reduction of incidence of preoperative microembolic signals

This endpoint is to evaluate whether the rate of patients with incidence of preoperative microembolic signals (MES) was reduced (from Visit1 to Visit 3). Compared will be patients who have been treated with Revacept plus antiplatelet therapy (aspirin or clopidogrel) versus antiplatelet therapy alone (placebo) prior to carotid endarterectomy (CEA). MES data from the central reading lab ([name], Münster) are evaluated.

The evaluation will be performed using a two-sided test of superiority. Groups will be compared for the combined centers using Fisher's exact test.

The sequence of a priori defined hypotheses, with  $\pi$  rate of patients with MES V3 < MES V1 for the specified group, will be:

1)  $H_{01}: \pi_{\text{Revacept 120 mg}} = \pi_{\text{Placebo}}$  VS.

$H_{A1}: \pi_{\text{Revacept 120 mg}} > \pi_{\text{Placebo}}$

2)  $H_{02}: \pi_{\text{Revacept 40 mg}} = \pi_{\text{Placebo}}$  VS.

$H_{A2}: \pi_{\text{Revacept 40 mg}} > \pi_{\text{Placebo}}$

3)  $H_{03}: \pi_{\text{Revacept 120 mg}} = \pi_{\text{Revacept 40 mg}}$

$H_{A3}: \pi_{\text{Revacept 120 mg}} > \pi_{\text{Revacept 40 mg}}$

4)  $H_{04}: \pi_{\text{Revacept 120 mg + 40 mg}} = \pi_{\text{Placebo}}$  VS.

$H_{A4}: \pi_{\text{Revacept 120 mg + 40 mg}} > \pi_{\text{Placebo}}$

Each hypothesis will be tested using Fisher's exact test.

With the first two and the last of hypotheses the test product for a given dose level or overall will be tested against Placebo. With the third hypothesis the higher dose level of the test product will be compared against the lower dose of the test product.

Statistical Analysis Plan  
Test product: Revacept  
EudraCT number: 2011-001006-10  
Date 10.06.2019

All tests will be interpreted exploratively.

The between group risk difference and its 95% confidence interval (CI) will be estimated for each group comparison.

The prime analysis will be based on the ITT population. The PP population will be used for the supportive analyses.

In a subgroup analysis, only patients will be compared who did not receive any change in the concomitant medication with anti-platelet activity (=rescue medication) between the initial assessment at V1 and the follow-up investigation at V3 / V5.

Additionally the prevalence / rate of patients with microembolic signals (>0) at Visit 3 will be compared in a similar manner as in the hypothesis 1- 4

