Missing values for the primary analyses at Visit 3 will be imputed by the last observation carried forward approach. This means patients who dropped out before Visit 3 will be counted as non-responder.

An additional analysis of the first endpoint will be performed including the factor center as a stratum. Fisher's exact test will be performed for each stratum and meta-analysis approach will be chosen. Centers with less than 3 patients will be combined into a 'small number of patients' combined stratum.

Individual center results will be presented in a graphical overview with risk differences and their confidence intervals.

**In case of heterogeneities in the baseline parameters**, sensitivity analyses will be performed for the first endpoint using Fisher's exact test and by including the respective parameter as a stratum (binary, ordinal or categorical data). For continuous data these data will be transformed into classes before used as stratum.

A meta-analysis approach will be chosen to pool the stratum dependent results and to investigate for heterogeneity in the strata (e.g. Whitehead, 2003).

The following baseline parameters will be used for the analysis of heterogeneity:

- Demographics
  - Age
  - Height
  - Weight
  - Ethnic origin
  - Gender
  - Hormone status
- Anamnesis – Medical history
  - Number of patients with previous diseases and surgeries
- Vital signs
  - systolic and diastolic blood pressure (right and left arm)

- Physical examination
  - Abnormal findings of assessment of heart, lung, abdomen and oedema (Yes/No)

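### The lead MES responder rate scores every patient with no MES at Visit 1 as a non-responder, so its risk difference is diluted, and related change measures lack a zero-baseline rule

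*SAP*

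**What the plan says.** The lead efficacy comparison in SAP 8.4.1 uses the "rate of patients with MES V3 < MES V1 for the specified group", tested pairwise with Fisher's exact test and reported as a risk difference with a 95% interval. On the analysis set it says: "The prime analysis will be based on the ITT population". SAP 6.2 defines that set: "all subjects who have had at least one dose of medication will be included in the ITT analysis".

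SAP 8.2.8 explains how patients without MES entered the trial: "Due to high rate of no microembolic signals we abandoned the criterion" that had made them ineligible, and "In the further course of the study patients were included irrespective whether they present with microemboli or not". The inclusion criteria in Protocol 5.2.1 contain no MES requirement.

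Other planned measures bear on the point:

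- SAP 8.4.1 adds a second binary comparison: "Additionally the prevalence / rate of patients with microembolic signals (>0) at Visit 3 will be compared".
- SAP 8.4.2 compares the absolute and the percent change in MES from Visit 1 to Visit 3.
- SAP 8.4.4 compares the absolute and percent change in DWI lesion count, any and new lesions at Visit 5, and the share of patients whose lesions were reduced.
- SAP 8.2.9 provides a baseline class of 0 DWI lesions, so a zero baseline is foreseen.

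Visit 1 MES is not among the randomisation factors (Protocol 6.1.7, SAP 3.1), nor in the list of baseline parameters for the heterogeneity analyses in SAP 8.4.1.

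**The concern.** The responder definition presumes that there is something to reduce. MES counts cannot fall below zero, so a patient who starts at zero is a non-responder whatever the treatment does. A patient who stays at zero and one who goes from zero to ten score alike. These patients remain in the denominator of every arm and pull the risk difference towards zero by an amount that depends only on how many there are.

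The study is exploratory (SAP 7.5), so no confirmatory claim is at risk. The estimate and its interval are the main product, and the Protocol synopsis foresees combining the data with future studies. A risk difference scaled by the local share of MES-positive patients cannot be compared with a trial that enrolled only such patients, nor read as the effect in patients with emboli. For the two percent changes, the programmer would have to decide how to treat a zero denominator without guidance from the plan.

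**Working it through.** **Inputs from the documents.** Responder definition and 95% interval: SAP 8.4.1. All dosed patients: SAP 6.2. Planned size, 50 per arm: SAP 3.3. Two-sided tests: SAP 8.4. The figure of 50 cannot be reproduced, because no rates, alpha or power are given; nothing below depends on reproducing it.

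**Assumed inputs.** f, the share of patients with Visit 1 MES > 0, from 80% down to 15%. Response among MES-positive patients of 30% on placebo and 60% on Revacept. Two-sided alpha 0.05.

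**Step 1: dilution.** With p the response rate among positives, the ITT rate is f × p + (1 − f) × 0 = f × p. With equal f in both arms, RD(ITT) = f × (p_R − p_P). At f = 40% this is 0.4 × 0.60 − 0.4 × 0.30 = 24% − 12% = 12 points. This step is an identity; only the numbers are assumed.

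**Step 2: unequal f.** In general RD(ITT) = f_R × p_R − f_P × p_P. With no drug effect, 50% response in both arms and f of 30% v 20%, the result is 15% − 10% = 5 points. Under simple randomisation the SD of f_R − f_P is √(2f(1 − f)/50). At 45% response in both arms, one SD moves the risk difference by 0.45 times that. At 30% v 60%, imbalance in f contributes Σp²f(1 − f) / Σpf(1 − pf) of the variance. At f = 40% this is 0.45 × 0.24 / (0.1056 + 0.1824) = 0.108/0.288 = 37.5%.

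**Step 3: precision.** The Wald 95% half-width is 1.96√(0.45/(50f)) among positives and 1.96√(Σpf(1 − pf)/50) in ITT. At f = 40% these are 1.96√(0.45/20) = 29 points and 1.96√(0.288/50) = 15 points. Power is exact two-sided Fisher.

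| One dose v placebo, 50 per arm | f = 80% | 60% | 40% | 25% | 15% |
|---|---|---|---|---|---|
| ITT risk difference (30 among positives), points | 24 | 18 | 12 | 7.5 | 4.5 |
| ITT half-width, points | 18 | 17 | 15 | 12 | 10 |
| V1-positive half-width, points | 21 | 24 | 29 | 37 | 48 |
| Power, ITT rule, % | 64 | 45 | 26 | 12 | 5 |
| Power, V1-positives only, % | 73 | 56 | 35 | 21–26 | 8–13 |
| SD of imbalance in f, points | 8.0 | 9.8 | 9.8 | 8.7 | 7.1 |
| Resulting shift in RD at 45% response, points | 3.6 | 4.4 | 4.4 | 3.9 | 3.2 |
| Share of variance from imbalance, % | 17 | 29 | 37.5 | 43 | 46 |

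The power ranges in the last two columns arise because 50f is 12.5 and 7.5 patients, taken as 12–13 and 7–8.

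**Step 4: the Visit 3 prevalence comparison.** This is defined at a zero baseline but counts only complete clearance. At f = 40% with no new emboli, its power is 23% if every reduction is complete and 7% if half are partial, so it cannot stand in for the responder rate. Stratifying it by Visit 1 status does help. Assume 15% v 30% of positives cleared and 10% new emboli in both arms. At f = 40% the Visit 3 rates are 0.4 × 0.85 + 0.6 × 0.10 = 40% and 0.4 × 0.70 + 0.6 × 0.10 = 34%. The unadjusted SD of the difference is √((0.40 × 0.60 + 0.34 × 0.66)/50) = 9.6 points. With stratification it is about √((0.4 × 0.3375 + 0.6 × 0.18)/50) = 7.0 points, where 0.3375 = 0.85 × 0.15 + 0.70 × 0.30 and 0.18 = 2 × 0.10 × 0.90.

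**Step 5: change measures.** Percent change is (later − V1)/V1, which has no value at V1 = 0. A reduction in DWI lesions is computable at a zero baseline but can never occur, so the fault there is the denominator, as for MES.

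**The case against.** The strongest reply is that the ITT rate is a legitimate quantity, that both documents make ITT the first-line efficacy analysis, and that randomisation protects its null. This stands: a reader might infer that the planned test is biased or should be replaced, and the documents support neither. Chance imbalance in f is lost precision, which the planned interval already reflects under simple randomisation. The imbalance figures may also be too large, because allocation is by minimisation on prior antiplatelet therapy, statin therapy and degree of stenosis. If those factors predict Visit 1 MES, the imbalance shrinks.

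A reader might also infer that f would go unreported. That goes too far. MES incidence before and after treatment is a listed objective (Protocol 3, SAP 2), and SAP 8.4.2 summarises Visit 1 MES. What is missing is an explicit line giving the share by arm next to the lead result.

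A third tempting reading is that the missing-data rule contradicts itself for a patient with zero MES at Visit 1. The rule reads "Missing values for the primary analyses at Visit 3 will be imputed by the last observation carried forward approach" and then "This means patients who dropped out before Visit 3 will be counted as non-responder". For the lead responder rate the two sentences agree, since carrying Visit 1 forward gives no reduction. The rule is confined to the primary analyses, so for the additional Visit 3 prevalence comparison the plan is silent, not contradictory.

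Finally, several planned measures are already defined at a zero baseline: Visit 3 prevalence, absolute changes, and any or new DWI lesions. They soften the problem. None is stratified by Visit 1 MES status, so none gives the effect in patients with emboli.

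**Conclusion.** The point holds as one of interpretation and precision. The lead risk difference is the effect among MES-positive patients multiplied by their share, exactly so when that share is equal across arms. With an assumed 30-point effect it would read as 24 points at f = 80% and 4.5 points at f = 15%. The dilution follows from the definition alone. Its size rests on f and the response rates, which the documents do not give, and the imbalance figures rest on simple randomisation. The two percent changes have no value at a zero baseline and no rule is stated; the rate of reduced DWI lesions shares the denominator fault. Since the study is exploratory and the null is preserved, this is no threat to validity. It is worth correcting before unblinding because it governs how the first efficacy result will be read.

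**What to change.** In the updated SAP that SAP 1 places in the Blind Review Report, before the blind is broken:

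1. Keep the all-ITT responder rate. Beside it, report the same rate among patients with Visit 1 MES > 0, and reduced DWI lesions among patients with at least one Visit 1 lesion, with denominators by arm.
2. Stratify the planned Visit 3 prevalence comparison by Visit 1 MES (0 v > 0) with the Cochran-Mantel-Haenszel procedure that SAP 8.4.6 already uses, and add Visit 1 MES to the heterogeneity list in SAP 8.4.1.
3. Restrict percent change in MES and DWI lesions to non-zero baselines. For all patients, rely on the planned absolute changes, with the Wilcoxon analysis that SAP 8.4 provides where normality fails.
4. Show the Visit 1 MES-positive share by arm with the lead result.
5. As a minor point, state how a missing Visit 3 recording is scored in the prevalence comparison.

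The cost is wording and some programming; no new data or patients are needed. The price is wider intervals in the added table, with half-widths of about 21 to 48 points for one dose v placebo as f falls from 80% to 15%. The gain in power there is moderate at best (for example 26% to 35% at f = 40%), so the table serves interpretation more than detection.

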7.2.7. Transcranial Doppler

Central Analysis & Test Run

Each study centre shall send a test dataset to the central core laboratory prior to starting patient recruitment. The core lab will notify the study centre and sponsor of successful completion of a test run. TCD recordings are to be sent to the following core lab for central analysis:

PD Dr. med. [name]
Facharzt für Neurologie
[name]
[name]
[contact]
[contact]

Central analysis will be performed for both TCD datasets recorded for each patient enrolled (i.e. visit 1 and 3).

There is no need for local analysis of TCD recordings. Both TCD recordings are analysed centrally only.

MES detection by TCD

TCD recordings will be made from the middle cerebral artery (MCA), via the trans-temporal route. Each TCD assessment is recorded for one hour as specified below.

All TCD recordings must be performed under similar conditions, i.e.:

- Same apparatus
- Same position of patient
- System settings

All recordings shall be performed with a DWL TCD machine with single-depth 2-MHz transducers. Standard settings should be used. Machine settings shall be adapted to harmonised consensus guidelines (Ringelstein et al., 1998) and agreed upon by all study centers. For TCD recording, patients are to be placed in a sitting or supine position. The MCS will be identified via transtemporal window and a transducer will be attached using a

standard headset. TCD signals are recorded for one hour. The total number of MES per hour will be analysed.

Spectral display and audio signals will be monitored acoustically and visually online by an experienced observer during all recordings. Audio and visual signals will be recorded onto suitable storage media for central analysis.

MES will be identified visually as predominantly unidirectional short-duration intensity increase accompanied by characteristic acoustic clicking, chirping or moaning sounds. A previously agreed threshold will be set at all participating study centres following validation by analysis of standard reference tapes. MES intensity will be measured in dB and be calculated as the ratio of peak intensity of MES divided by the intensity of the background signal. The same algorithm will be used throughout the study. Central offline analysis of all recordings will be performed using the same machine and same algorithm.

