## **3.3 Sample size**

Primary sample size estimation was conducted based on the CARESS study results (Markus et al., 2005). 50 patients should be allocated to each treatment arm. Due to low incidence of MES (high screening failure rates) study design was changed to exploratory study (Version 8 of the study protocol).

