### 8.4.2 Rate of MES per hour (before and after treatment, before CEA)

The rate of MicroEmbolic Signals (MES) as assessed at Visit 1 and at Visit 3 will be summarized using descriptive statistics. Data will be analysed from the central reading lab.

Groups will be compared for

- difference of MES at Visit 1 versus post treatment at Visit 3 (delta MES) and
- percent change of MES at Visit 3 compared to Visit 1 (delta MES)

using the ANOVA.

In a subgroup analysis, only patients will be compared who did not receive any change in the concomitant medication with anti-platelet activity (=rescue medication) between the initial assessment at V1 and the follow-up investigation at V3 / V5.

In addition normality of distribution will be checked based on goodness of fit tests. If normality can not be assumed sensitivity analysis will be performed using the Wilcoxon test.

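### The first-listed MES endpoint (any fall from Visit 1 to Visit 3, all ITT patients) uses the recordings insensitively; a baseline-adjusted count analysis should lead

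*SAP*

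**What the plan says.** SAP 8.4.1 is the first efficacy analysis. The tested quantity is the "rate of patients with MES V3 < MES V1 for the specified group", with no minimum fall and no Visit 1 threshold. Four contrasts are compared by Fisher's exact test in the ITT set: 120 mg v placebo, 40 mg v placebo, 120 mg v 40 mg, and both doses pooled v placebo. On sidedness, "The evaluation will be performed using a two-sided test of superiority", although the alternatives are written in one direction. On estimation, "The between group risk difference and its 95% confidence interval (CI) will be estimated for each group comparison". The share of patients with any MES at Visit 3 is an additional comparison.

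Each visit supplies one recording. Protocol 7.2.7: "TCD signals are recorded for one hour".

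SAP 8.2.8 records that the requirement for a signal at screening was dropped during the study, so later patients entered with or without MES. SAP 8.4.1 does not restrict its denominator to patients with MES at Visit 1.

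SAP 8.4.2 compares groups by ANOVA on the "difference of MES at Visit 1 versus post treatment at Visit 3 (delta MES") and on percent change, with Wilcoxon as a sensitivity analysis if normality fails. It has no baseline-adjusted, log-scale or ratio analysis. SAP 7.5, 8.4 and 8.4.1 make every test exploratory.

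**The concern.** Under this definition a fall from 10 to 9 signals scores the same as a fall from 10 to 0, and a rise from 5 to 50 scores the same as no change. Two single-hour counts at the same true rate will often differ, so many untreated patients who had signals at Visit 1 will be called responders. Patients with a zero count at Visit 1 cannot fall and are non-responders whatever the drug does.

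An exploratory dose-finding trial is there to estimate effects for the next study. If its first-listed MES result is a diluted risk difference with low sensitivity, a real reduction may look unremarkable in the place where readers look first, and worsening does not show at all.

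**Working it through.** **What can be reproduced.** SAP 3.3 states "50 patients should be allocated to each treatment arm" and "Primary sample size estimation was conducted based on the CARESS study results", but gives no alpha, power, effect or control rate. The 50 per arm therefore cannot be reproduced and is not called wrong here.

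**Inputs from the documents.** V3 < V1; one hour per visit; 50 per arm; ITT denominator including Visit 1-negative patients. On prevalence the SAP says only "Due to low incidence of MES (high screening failure rates) study design was changed to exploratory study".

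**Assumed inputs.** Alpha is two-sided 0.05 (not stated, but 95% CIs are planned). Visit 1-positive share is 25, 40 or 60%, with mean 1, 2 or 3 MES per hour. The true rate ratio is 0.5. No Visit 3 recording is missing.

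**Step 1: response by chance.** For two independent Poisson counts with the same mean λ, V3 < V1 already implies V1 > 0, so

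P(V3 < V1 | V1 > 0) = ½ × (1 − P(tie)) / (1 − e^−λ), with P(tie) = e^−2λ I₀(2λ).

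At λ = 1: P(tie) = 0.3085, half the remainder is 0.3457, and 0.3457 / 0.6321 = 0.55. The halved-rate row sums P(V1 = k) × P(V3 ≤ k − 1) over k ≥ 1, with mean λ/2 at Visit 3, and divides by 1 − e^−λ.

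| λ per hour | 0.5 | 1 | 2 | 3 | 5 | 10 | 20 |
|---|---|---|---|---|---|---|---|
| unchanged rate | 0.68 | 0.55 | 0.46 | 0.44 | 0.44 | 0.46 | 0.47 |
| halved rate | 0.82 | 0.74 | 0.70 | 0.72 | 0.77 | 0.88 | 0.96 |

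At 0.3 per hour the unchanged-rate figure is 77%. If rates also vary between patients (gamma-Poisson) it is 49–55%; with extra within-patient visit-to-visit variance of 0.5 it is 55–62%.

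**Step 2: what the ITT test sees.** With 25/40/60% Visit 1-positive, no extra variance and a halved rate, the response rates are 20/32/47% on drug and 13/20/30% on placebo.

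**Step 3: power.** Patient rates follow a gamma distribution whose shape k solves 1 − (k/(k+m))^k = positive share, where m is the mean. There were 500 simulated trials per setting, so the simulation error is at most about √(0.5 × 0.5 / 500) = 2 percentage points. The last column is a second set of assumed rates spanning 30–62% positive.

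| 50 v 50, rate halved | 25% | 40% | 60% | second set |
|---|---|---|---|---|
| Fisher, V3 < V1, ITT (lead) | 10% | 17% | 35% | 11–37% |
| Fisher, fall of at least half, ITT | 11% | 26% | 50% | – |
| Fisher, V3 < V1, Visit 1-positives only | 20% | 37% | 59% | 24–69% |
| Wilcoxon on change (SAP 8.4.2) | 31% | 50% | 73% | 34–86% |
| ANCOVA, log(1+V3) on log(1+V1) | 43% | 63% | 87% | 43–89% |

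With extra visit-to-visit variance of 0.5 (column labels are shares before it is added), the lead test has 4/8/16%, Wilcoxon 16/25/40% and ANCOVA 24/35/54%. The second set gives 6–15% for the lead test and 26–60% for the adjusted log count. With variance of 2, ANCOVA itself has only 10/18/26%.

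With no drug effect, Fisher rejected in about 2–4% of trials and ANCOVA in 4.5–6.1%, so inflated error does not explain the gap.

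**Step 4: where the loss comes from.** Restricting the lead test to Visit 1-positives recovers (20 − 10)/(43 − 10) = 30%, (37 − 17)/(63 − 17) = 43% and (59 − 35)/(87 − 35) = 46% of its gap to ANCOVA. The rest is lost by dichotomising. If every patient were Visit 1-positive, the lead test would have 70% v 93% for ANCOVA (mean 2 per hour) or 91% v 99% (mean 5).

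**Step 5: ceiling.** With 25% Visit 1-positive, 50% chance response and a drug that abolishes every signal, the lead test compares 25% with 12.5%. By normal approximation its power is 36%, and 80% would need 152 per arm.

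**The case against.** The strongest reply is that nothing depends on this test. Protocol section 3 lists the efficacy endpoints without ranking them, the protocol synopsis plans no formal hypothesis testing, and SAP 8.4.1 itself asks for exploratory interpretation. The change in MES is already compared in 8.4.2, so the information is not lost. This stands, and it makes the point an improvement rather than an error that invalidates the study. It does not remove the point: 8.4.1 comes first, is called the first endpoint, and carries the ordered hypotheses and the planned risk differences.

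A reader might infer three stronger things that the documents do not support.

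- **That chance responders bias the comparison or produce false positives.** They arise equally in randomised arms, and the simulated error rate is below 5%. Regression to the mean affects the change score too, so it does not favour one endpoint over the other.
- **That the one-signal rule alone explains the power gap.** Step 4 shows that the Visit 1-negative denominator contributes a large part. Raising the threshold to a halving within ITT moves power only from 10/17/35% to 11/26/50%.
- **That a real halving would be reported as no difference.** That assumes that 8.4.2 and the confidence intervals would be ignored.

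The power figures also rest on assumed rates. With substantial visit-to-visit variation, the adjusted analysis too would usually miss a halving when few patients are positive.

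**Conclusion.** The point holds as a matter of sensitivity. The chance-response figure needs only a counting model: 44–68% under Poisson at 0.5–20 per hour, and about half or more under the gamma-Poisson settings. The power figures are conditional on assumed prevalence, rates and effect. With a halved rate and 25–60% of patients Visit 1-positive, the lead test has about 10–35% power against 43–87% for the adjusted log count of the same recordings (11–37% against 43–89% in the second set). The ordering of these two tests held in every mixed-population setting with a true effect; the size of the gap depends on the inputs. The loss is due jointly to dichotomising and to keeping Visit 1-negative patients in the denominator. The comparison is unbiased, the study is exploratory, and a weaker but useful count analysis is already planned. The change is worth making because it is cheap and more precise, not because the present plan gives a wrong answer.

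**What to change.** Before unblinding, make the lead MES analysis a baseline-adjusted count analysis of Visit 3 on Visit 1 for the four contrasts in 8.4.1. One option is a negative binomial model with log(V1+1) as covariate, reporting the rate ratio with 95% CI, and a rank or log(1+MES) ANCOVA as sensitivity analysis. The powers above are for the log-count ANCOVA, not the negative binomial model. With many zeros and 50 per arm the latter may fail to converge or give intervals that are somewhat too narrow, so name the fallback in advance.

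If log(1+MES) is reported, label the result a ratio of geometric means of (1+MES). It is not a rate ratio: a true halving gives about 0.72–0.87 on that scale.

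Keep V3 < V1 as a supportive table among Visit 1-positive patients, with the placebo rate as the reference for chance response and the number of patients with a rise beside it.

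Swapping the order of 8.4.1 and 8.4.2 would not be enough, because 8.4.2 contains no such model and its percent change is undefined when V1 = 0. The cost is one new model written into 8.4.2 and a headline that is a ratio rather than a percentage of patients. No new data are needed and there is no alpha to reallocate. Protocol 9.3 and SAP section 1 both provide for an updated SAP at blind review, before the code is broken.

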### 8.2.1 Demographics

Demographic variables will be evaluated from the Screening assessment (Visit 1).

- Continuous demographic variables (age, height, weight) will be summarized using usual descriptive statistics.
- Nominal data (ethnic origin, gender and hormone status) and ordinal data (age classes) will be summarized by means of absolute and percent numbers.

A homogeneity analysis will be performed for the ITT and PP population.

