### **8.2.2 Baseline characteristics – Anamnesis**

The following categorical baseline data will be analyzed descriptively by means of absolute and percent numbers

- Medical history  
Pre-existing diseases including surgeries/interventions for the last 3 months will be described presenting
  - number and percent of patients with previous diseases or surgeries if documented
  - frequency distribution of diseases and surgeries as reported by the investigator

and will be summarized by means of frequency tables.

A homogeneity analysis will be performed for number of patients with previous diseases or surgeries for the ITT and PP population using statistical tests as appropriate.

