### **8.2.3 Baseline characteristics – Physical examinations**

- Results of physical examination, assessment of
  - heart (normal/abnormal)
  - lung (normal/abnormal)
  - abdomen (normal/abnormal)
  - oedema (normal/abnormal)

will be described presenting number and percent of patients with abnormal findings and summarized by means of frequency tables.

A homogeneity analysis will be performed for physical assessment (using Fisher's exact test) for the ITT and PP population.

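### An undefined baseline-imbalance trigger decides which stratified sensitivity analyses of the first MES endpoint are run, so chance largely selects the adjustments

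*SAP*

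**What the plan says.** The prime analysis of the first endpoint (SAP 8.4.1) is an unstratified Fisher's exact test in the ITT population, with PP as support. A centre-stratified analysis is also planned unconditionally. A further set of stratified analyses is conditional: it is run "In case of heterogeneities in the baseline parameters", using the variable concerned as the stratum. For continuous variables the SAP adds: "For continuous data these data will be transformed into classes before used as stratum". It gives no class limits.

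The eligible variables are introduced by "The following baseline parameters will be used for the analysis of heterogeneity". They are age, height, weight, ethnic origin, gender, hormone status, previous diseases and surgeries, systolic and diastolic blood pressure on each arm, and abnormal findings for heart, lung, abdomen and oedema.

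SAP 8.2 plans between-arm tests of the same variables in the ITT and PP populations:
- Demographics (8.2.1): a homogeneity analysis with no test named.
- Medical history (8.2.2): a homogeneity analysis "for the ITT and PP population using statistical tests as appropriate".
- Examination (8.2.3): "A homogeneity analysis will be performed for physical assessment", by Fisher's exact test.
- Blood pressure (8.2.5, among the risk factors): Fisher, Wilcoxon or Mantel-Haenszel tests.

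Neither 8.2 nor 8.4.1 states a significance level or any other criterion for calling a variable heterogeneous.

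SAP 3.1 and protocol 6.1.7 name three factors used in the minimised allocation because they may be prognostic: prior antiplatelet therapy, prior statin therapy and degree of stenosis. None of them is on the 8.4.1 list, and neither is the visit 1 MES count.

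**The concern.** A sensitivity analysis shows whether the main result survives a different reasonable choice. It does this best when the alternative is fixed in advance. Here the alternative depends on an observed baseline difference. In a correctly randomised trial such a difference is a chance finding, and its p-value does not measure how far the MES comparison is distorted. Distortion depends on how strongly the variable relates to the outcome as well as on the size of the imbalance.

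Two faults follow. A listed variable can be adjusted for because it happened to differ. A variable with more bearing on the outcome can go unadjusted because it fell short of an unwritten threshold, or because it is not on the list at all. Baseline MES shows the second fault. The endpoint counts patients whose visit 3 count is below their visit 1 count, so a patient with no signals at visit 1 cannot respond. SAP 8.2.8 confirms that such patients were admitted after the entry rule was changed.

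The rule also cannot be applied at the blind data review, because a between-arm difference is visible only with treatment codes. As written, the stratifiers are therefore selected after unblinding. At stake is what the adjusted results for the first endpoint can be taken to show.

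**Working it through.** The documents give no figure for how often the trigger would fire, so there is none to reproduce. The question is how often at least one listed variable would be flagged when allocation is correct.

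**Inputs**
- Items (SAP 8.4.1): 6 demographic + 1 medical history + 4 blood pressures (systolic and diastolic, right and left) + 4 examination findings = 15. Counted as printed entries, with blood pressure and examination as one each: 6 + 1 + 1 + 1 = 9.
- Level α: not stated. 5% is assumed, and other levels are shown.
- Arms: three, planned at 50 each (SAP 3.3).
- One test per item, in one analysis set.

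**Independent tests**

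P(at least one flag) = 1 − (1 − α)^k. The expected number of flags is kα.

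With k = 15 and α = 0.05: 15 × 0.05 = 0.75 flags expected, and P = 1 − 0.95^15 = 1 − 0.463 = 0.537.

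Changing the level, with k = 15:

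| α | 1 − (1 − α)^15 |
|---|---|
| 0.01 | 0.140 |
| 0.05 | 0.537 |
| 0.10 | 0.794 |
| 0.20 | 0.965 |

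Changing the count, with α = 0.05:

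| k | Reading of the list | 1 − 0.95^k |
|---|---|---|
| 15 | every item separate | 0.537 |
| 12 | examination as one item | 0.460 |
| 10 | also blood pressure as two items | 0.401 |
| 9 | entries as printed | 0.370 |

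**Allowing for correlation and sparse exact tests**

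The 15 items are not independent. Blood pressure supplies four overlapping measures, and gender is tied to hormone status, height and weight. Exact tests of rare findings also reject less often than their nominal level. A simulation with no true differences (3 × 50 patients, 2,000 runs per scenario) used a Kruskal-Wallis test for continuous items and an exact 2 × 3 test for binary items, all at 5%. The correlations and prevalences are assumptions, not figures from the documents.

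| Scenario | Right/left BP correlation | Systolic/diastolic correlation | Abnormal findings | At least one flag |
|---|---|---|---|---|
| Mild | 0.80 | 0.5 | 15–20% | 45.0% |
| Middle | 0.90 | 0.6 | 5–10% | 41.8% |
| Strong, sparse | 0.95 | 0.7 | 3% | 36.8% |

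The simulation standard error is about 1.1 percentage points: √(0.418 × 0.582 / 2000) = 0.011. In the sparse scenario each examination finding was flagged in only 1.4% to 2.8% of runs, which is part of why the total falls below 54%.

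**The case against.** The case on the other side has several parts.

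- **The trigger is inferred.** The SAP never says that a significant homogeneity test is what counts as heterogeneity. This stands as a caution. The inference is still reasonable: 8.2 tests these same variables and no other criterion is offered.
- **54% is not a property of this SAP.** A reader might take it as the trigger rate. It needs a 5% level that the SAP does not state and 15 independent tests, which these are not. This stands, and the figure belongs only at the top of a range.
- **Timing of class limits.** A reader might infer that the limits will be chosen after the differences are seen. The documents do not say so. SAP 8.2.1 already mentions age classes, and SAP section 1 puts the final SAP in the Blind Review Report, completed before the blind is broken. What can be said is that no limits are given and nothing requires them to be fixed earlier.
- **Relevance of the variables.** A reader might infer that the listed variables are unrelated to MES. The documents cannot show that. They do show which factors the plan itself treats as potentially prognostic, and those are absent from the list.
- **Chance as the sole cause.** This holds for all randomised patients. The ITT set here means dosed patients, the PP set drops major deviators, and protocol 6.1.8 allows randomisations to be rejected and patients replaced. An imbalance in those sets may also reflect selection.
- **Small consequence.** The prime analysis is fixed, the triggered analyses are labelled as sensitivity analyses, and every test is exploratory. This stands in full. The further homogeneity tests in SAP 8.2.6, 8.2.7 and 8.2.9 (bleeding, ECG, DWI) cover variables outside the 8.4.1 list and do not feed the trigger.

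**Conclusion.** The point holds as a limited one. The conditional sensitivity analyses of the first MES endpoint follow a data-driven rule with no threshold and no class limits, and largely chance imbalance would select them. At an assumed 5% level, at least one adjustment would be triggered in roughly 37% to 45% of correctly randomised trials under the assumed correlations and prevalences. With 15 independent tests, 1% to 20% levels give 14% to 96%. That width comes from the missing threshold, which is the firmest part of the finding. The omission of the three minimisation factors and baseline MES is plain from the text.

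A reader might go further and conclude that the main MES result is compromised. The documents do not support that: the unstratified ITT comparison is run whatever the baseline table shows, and nothing is confirmatory. The change is worthwhile but minor.

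**What to change.** In SAP 8.4.1, remove the condition that starts the stratified analyses. State that the homogeneity tests in 8.2 are not used to select adjustments, and keep the descriptive baseline tables so that balance stays visible. Before unblinding, name a short list of sensitivity adjustments chosen for their expected relation to the endpoint, such as the three minimisation factors and baseline MES. Write down the classes for each, including the limits for baseline MES. Run and report all of them whatever the baseline table shows.

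No new data are needed. The cost is revised wording and a few fixed extra outputs. Some strata will be sparse: a two-level factor splits a planned arm of 50 into 25 per level on average, and an uneven split leaves fewer in one level. Taking the factors one at a time limits this.
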